#### **5.7.4 Change from baseline in Assessment of Caregiver Experience with Neuromuscular Disease**

Parents of subjects will complete the Assessment of Caregiver Experience with Neuromuscular Disease (ACEND) questionnaire at screening and on Days 169 and 456. This assessment instrument has been designed to quantify the caregiver impact experienced by parents of children affected with severe neuromuscular diseases, including children with SMA (Matsumoto et al. 2011).

The ACEND includes a total of seven domains assessing physical impact (including feeding/grooming/dressing, sitting/play, transfers, and mobility) and general caregiver impact (including time, emotion, and finance) and each domain comprises several items. The total score for a domain with  $n$  items, each item assessed on ordinal scale from 1 to  $z$ , is derived as follows: 100 multiplied by (Mean of the  $n$  items in the domain -1) divided by  $(z-1)$ . This total score will be on a scale of 0 to 100 with a higher score indicating a greater impact on the caregiver. At least two items for the time domain and one item for the remaining domains need to be non-missing for a total to be calculated; else the total score will be set to be missing.

The change and percentage change from baseline for each domain will be presented by visit and treatment group. An ANCOVA model will be used to analyze the change and percentage change from baseline through to 15 months with missing data handled by multiple imputation as was described for PedsQL. Similarly, plots of the mean and percentage change from baseline over time, based on the ANCOVA model will be provided by treatment group.

Analyses will be conducted on the ITT Set and PPS.

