### *Multiple imputation analysis methods*

For the HFMSE, PedsQL, ACEND, upper limb module the imputations will be performed on the ITT population. In any sensitivity analyses using multiple imputation such as repeating the main analysis in the PPS the subset of subjects in the PPS will be selected from the multiple imputed datasets obtained from the ITT population. If the MI procedure imputes any

values outside the expected range for the scale e.g. from 0 to 66 for HFMS-E then values below 0 will be set to 0 and values above 66 will be set to be 66.

For each of the 100 imputed datasets, the endpoint will be compared between treatment groups using an ANCOVA model for continuous endpoints or logistic regression for binary endpoints as described in the main analysis for each endpoint. The estimates from the 100 fitted models will be combined to provide an overall estimate with corresponding confidence intervals and p-value [Little et al, 2002].

For the continuous endpoints, the difference between treatments and the corresponding CI will be presented. In addition, for each subject the median change from baseline to each visit will be calculated across the multiple datasets and summarized by treatment group. For the analyses using logistic regression the odds ratio and corresponding CI will be presented. In addition, the estimates of the binomial proportions in each treatment arm and the differences between treatments will be presented (Ratitch, 2013).

If, due to a small sample size or other unforeseen scenario, the multiple imputation model does not converge or encounters computational difficulties, then the number of iterations will be increased. If the model still fails then a Mixed Effects Model with Repeated Measures will be used as the primary analysis as described in Section 5.5.1.2.

In the presentation of results from multiply imputed data, the number of subjects with missing data and the degree to which it is missing will be summarized.

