#### **5.7.3 Change from baseline in Pediatric Quality of Life Inventory**

Subjects will be evaluated using the Pediatric Quality of Life Inventory (PedsQL™) Measurement 4.0 Generic Core Scales and 3.0 Neuromuscular Module (Varni et al. 1999) at screening (the baseline assessment) and on Days 92, 169, 274, 365 and 456.

The questionnaires are specific to the age of the subject, and sites are instructed to get both subjects and caregivers to complete the same age specific questionnaire as was collected at baseline irrespective of whether or not the subjects cross an age boundary at a subsequent visit.

The PedsQL parent questionnaire is collected for children in the following age categories: 2-4, 5-7, 8-12 and 13-18 years. Four dimensions are collected: Physical, Emotional, Social and School functioning and each item is scored on a 5 point ordinal scale (0= Never, 1 = Almost Never, 2= Sometimes, 3 = Often, 4 = Almost Always). The PedsQL patient questionnaire is collected for children in the following categories: 5-7, 8-12 and 13-18. Similar dimensions and 5-point ordinal scale are used as for the parents but for subjects aged 5 to 7 years a 3-point ordinal scale is collected, omitting the response levels of 1 and 3.

In the neuromuscular module, one parent questionnaire is collected for all subjects irrespective of age with three dimensions: 'About my child's neuromuscular disease', 'Communication' and 'Family resources'. The same 5-point ordinal scale is collected for each question. The patient neuromuscular disease questionnaire is collected for subjects in the following age categories: 5-7, 8-12, 13 -18. The questionnaire for subjects aged 5-7 years uses the 3-point ordinal scale as above and has only one dimension - 'About my Neuromuscular disease'. The questionnaires for the remaining two age categories cover dimensions for 'Communication' and 'Family resources' and use the 5-point ordinal scale.

In scoring a dimension the first step is to reverse and linearly transform to a 0-100 scale (0 = 100, 1 =75, 2=50, 3= 25, 4= 0), so a higher score is indicative of a better health related quality of life. If greater than 50 percent of the items within a dimension are missing then the dimension score will not be computed, otherwise the mean score for the dimension will be calculated as the sum of items over the number of items answered.

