A psychosocial health summary score, constructed from three dimensions, will be calculated as the sum of items over the number of items answered in the emotional, social and school functioning scales. A total score will be calculated as the sum of all the items over the number of items answered on all the scales. If greater than 50 percent of the items are missing, then the summary score or total score will be set to be missing.

For the neuromuscular module, a score for each dimension and then total score will be calculated in the same manner, no health summary scores are evaluated.

For the generic PedsQL and neuromuscular module, the change and percentage change from baseline in the total score will be presented by visit and treatment group for both the parent and subject assessments. Similarly, the changes in the individual dimensions and health summary score will also be presented.

The change and percentage change from baseline score (each total score and parent/subject evaluation separately) to each visit will be analyzed using an ANCOVA model with treatment group as a factor and age at screening and baseline score as covariates. A statistical test for a treatment effect will be performed at Days 92, 169, 274, 365 and 456.

Multiple imputation as described in Section 5.3 will be used to impute missing post baseline values. The imputation will be performed separately for each dimension and total and psychosocial summary scores. Due to the age specific nature of these questionnaires, subjects aged 2-4 years would not be expected to complete the self-evaluation and if this is the case then imputations will not be performed and the subjects will be excluded from the analysis.

A plot of mean change from baseline (each questionnaire and parent/subject separately) based on the estimates from the ANCOVA model over time will be provided by treatment group.

Analyses will be conducted on the ITT Set and PPS.

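### SAP 5.7.4 models percentage change for ACEND domain scores that can be exactly 0 at baseline, where the outcome is undefined, and unstable just above 0

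*SAP*

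**What the plan says.** **ACEND (SAP 5.7.4).** Each of the seven domains is scored as 100 × (item mean − 1)/(z − 1), where items run from 1 to z. The SAP describes the result so: "This total score will be on a scale of 0 to 100 with a higher score indicating a greater impact on the caregiver". The time domain needs two answered items; for the others, "one item for the remaining domains need to be non-missing for a total to be calculated". The analysis is then: "An ANCOVA model will be used to analyze the change and percentage change from baseline through to 15 months". Model-based plots of mean and percentage change are also planned, on the ITT Set and the PPS.

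**PedsQL (SAP 5.7.3).** The model is similar: "The change and percentage change from baseline score (each total score and parent/subject evaluation separately) to each visit will be analyzed". Only the total scores get this treatment, and the only model-based plot is of mean change.

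**Missing data (SAP 5.3).** Missing scores are multiply imputed under a normal model. Imputed values outside the range of the scale are pulled back to its limits; at the lower end, "values below 0 will be set to 0".

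Neither document says what happens to percentage change when the baseline is 0, or whether change or percentage change is the main analysis for these scores.

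**The concern.** A percentage change divides by the baseline score. Where that score is 0 the outcome does not exist, so the model cannot be fitted to the full ITT Set as planned. The families left without an outcome are not a random subset. On a scale where higher means more burden, a baseline of 0 marks the least caregiver impact, and those families can only stay the same or get worse.

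Just above 0 the ratio exists but is erratic. A rise from 5 to 15 is +200% and a rise from 50 to 60 is +20%, for the same 10 points. A few low-baseline families can dominate the fit.

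The SAP plans the two analyses side by side without ranking them. If they disagree, a reader has no prespecified basis for preferring one.

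**Working it through.** **1. The plan's own power figure.** The documents give none for ACEND or PedsQL. The only one is for the HFMSE (protocol 10.2, SAP 9): 70 vs 35, difference 3, SD 4.4, two-sided 0.05, at least 90%. Here 3/(4.4 × √(1/35 + 1/70)) = 3.29, and Φ(3.29 − 1.96) = 0.909; the noncentral t with 103 df gives 0.904. It reproduces, but says nothing about ACEND.

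**2. Zero is attainable.** If every answered item is 1, the score is 100 × (1 − 1)/(z − 1) = 0 for any z. In six of the seven domains one answered item can be enough. Percentage change, 100 × (Y − B)/B, is then a division by 0.

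**3. Imputation does not fill it.** SAP 5.3 imputes missing scores. An observed baseline of 0 is not missing, so the ratio is undefined in all 100 datasets. A missing baseline imputed below 0 would be set to 0, so the usable sample could differ between datasets.

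**4. Cost of losing the zero-baseline families alone.** Take 84:42 from SAP 5.1 and assume an effect with 80% power. With a share f lost evenly from both arms, power = Φ((1.960 + 0.842) × √(1 − f) − 1.960):

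- f = 1%: 79.6%
- f = 5%: 78.0%
- f = 10%: 75.7%
- f = 20%: 70.7%

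**5. Cost of the ratio itself.** With additive error of SD s, percentage change at baseline B has SD of about 100 × s/B. For s = 12 that is 120 percentage points at B = 10 and 20 at B = 60. With purely proportional error (CV 0.3) it is about 30 in the control arm at every baseline.

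**6. Simulation.** ANCOVA on treatment, age and baseline; 84:42; 2,000 runs per cell; scores in 5-point steps limited to 0–100; latent baseline SD 20. The latent mean was shifted to produce each f. At f = 0 it was 60, with the lowest baseline raised to 5. Comparisons should therefore be made across a row. Effects, SDs and f are assumptions. Power in %:

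| Setting | f | Absolute, all | Absolute, nonzero only | Percentage, nonzero only |
|---|---|---|---|---|
| Effect −8, additive SD 12 | 0% | 93.0 | 93.0 | 85.1 |
| | 5% | 90.0 | 89.8 | 79.2 |
| | 10% | 89.3 | 88.6 | 76.8 |
| | 20% | 87.0 | 84.3 | 71.3 |
| Effect −20%, additive SD 12 | 0% | 99.9 | 99.9 | 95.2 |
| | 5% | 88.8 | 88.8 | 49.6 |
| Effect −17%, CV 0.3 | 0% | 84.9 | 84.9 | 87.1 |
| | 5% | 81.7 | 81.8 | 87.0 |
| | 20% | 68.8 | 68.8 | 73.9 |
| Same, plus additive SD 3 | 0% | 82.5 | 82.5 | 84.2 |
| | 5% | 78.2 | 78.4 | 76.0 |
| | 20% | 65.0 | 66.4 | 56.8 |

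Simulation error is about √(0.85 × 0.15/2000) = 0.8 points per cell. In the first setting at f = 20%, losing families costs 87.0 − 84.3 = 2.7 points and the ratio a further 84.3 − 71.3 = 13.0. At f = 0 the ratio alone costs 93.0 − 85.1 = 7.9. With no treatment effect and additive error, rejection rates were about 4–5% for all three analyses.

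**7. PedsQL.** Items are converted as "reverse and linearly transform to a 0-100 scale (0 = 100, 1 =75, 2=50, 3= 25, 4= 0"). A total of 0 needs every answered item at the worst level, with at least half the items answered.

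**The case against.** Four points can be made against this, and each stands in part.

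- **A reader might infer that the SAP drops zero-baseline families, and does so silently.** It does not say so. What follows from the text is narrower: these families have no outcome value, so they are left out or handled by a rule not yet written. Nor need it be silent. SAP section 3 generally reports the number with data, and 5.3 calls for missingness to be summarized with imputed results.
- **A reader might infer that power falls because families are lost, and always falls.** Steps 4 to 6 show that losing them costs little at plausible shares. The larger loss comes from small nonzero baselines under additive error, and it reverses under purely proportional error.
- **A reader might treat PedsQL as equally exposed.** The percentage-change model there is limited to total scores, where 0 is improbable, and no percentage-change plot is planned.
- **Zero baselines may be rare for ACEND too.** Eligible children have never walked independently, so scores near 0 for transfers or mobility are not obviously common. The documents give no baseline ACEND data for these or the other domains.

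It is also fair that absolute and relative change are different quantities and may legitimately disagree, and that absolute change is already planned for the same scores. None of this supplies a value for percentage change at a baseline of 0.

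**Conclusion.** The point holds for ACEND as a defect in the planned calculation. Zero is a permitted baseline, percentage change is undefined there, imputation does not repair it, and ratios just above 0 are unstable.

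The size is uncertain. Under additive error and the assumed inputs, percentage change loses about 8 points of power with no zero baselines (93% vs 85%) and about 16 at a 20% share (87.0% vs 71.3%). Under purely proportional error it gains about 2 to 5 points. A general claim of lost power is therefore not supported.

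For PedsQL totals the problem is possible but improbable. ACEND and PedsQL are tertiary endpoints without multiplicity adjustment, and baseline-adjusted absolute change loses no family to this problem. No confirmatory conclusion is affected. This is a minor correction, worth making because it is nearly free.

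**What to change.** In SAP 5.7.4, make baseline-adjusted absolute change the only modelled and tested ACEND analysis, and remove the percentage-change ANCOVA and its model-based plot. If percentage change is kept, including in the by-visit summaries, make it descriptive, limit it to families with a nonzero baseline, and report how many are excluded per domain and arm.

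For consistency, in SAP 5.7.3 name absolute change as the main analysis for the PedsQL total scores.

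No new data or methods are needed, and there are fewer outputs to program. The price is the modelled relative-change result for one tertiary endpoint.

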### 5.7.5 Disease-related hospitalizations and adverse events

A blinded medical review of the adverse events will be conducted in order to define those events which would be considered disease related. The adverse event page in the CRF captures if an event is serious and one of the criteria of a serious event is if inpatient hospitalization required or hospitalization is prolonged.

The number of disease related adverse events, and as a separate analysis the subset of these events which required hospitalization will be analyzed using the rate at which they occur.

For descriptive purposes, the aggregate rate will be calculated for each treatment group by dividing the total number of events that occurred in a group by the total number of subject-years on study.

Annualized event rate will be calculated for each subject as the number of events that the subject experienced divided by the number of days on study and this ratio multiplied by 365.

Although disease related adverse events occur as a stochastic process, and can be assumed to be from a Poisson distribution, studies in other therapeutic areas have shown that data of this type are typically over-dispersed, i.e., the variation seen is greater than that predicted by the Poisson model. To account for over-dispersion in the annualized rate of events, the negative binomial distribution will be used. Thus, on the basis of event rate, treatment groups will be compared using a negative binomial model adjusting for the stratification factor, age at screening. An “offset” parameter, the logarithm of the time on study, will be included in the model. If the data are underdispersed, or if the negative binomial regression model does not converge, a Poisson regression model with the same covariate will be used instead of the negative binomial regression model. Dispersion will be evaluated from the Pearson chi-squared statistic.

Analyses will be performed on the ITT Set and PPS.

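### SAP 5.7.5: the non-convergence fallback to Poisson regression states no correction for the over-dispersion that the section itself expects

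*SAP*

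**What the plan says.** SAP 5.7.5 analyses two event counts: disease-related adverse events as identified by blinded medical review, and those among them that required hospitalisation. It notes that "studies in other therapeutic areas have shown that data of this type are typically over-dispersed", meaning that "the variation seen is greater than that predicted by the Poisson model". For that reason, "To account for over-dispersion in the annualized rate of events, the negative binomial distribution will be used". On covariates, "treatment groups will be compared using a negative binomial model adjusting for the stratification factor, age at screening", and for the offset "the logarithm of the time on study, will be included in the model".

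The fallback rule has two separate triggers, either of which is enough. One is underdispersion in the data. The other reads "if the negative binomial regression model does not converge, a Poisson regression model with the same covariate will be used instead of" that model. The section then adds: "Dispersion will be evaluated from the Pearson chi-squared statistic". It mentions no scale parameter, quasi-likelihood, sandwich variance or second attempt at the fit.

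The endpoint is listed as tertiary (SAP 1.1), and tertiary analyses carry no multiplicity adjustment (SAP 5.2). The analysis is run on both the ITT Set and the PPS.

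**The concern.** The first trigger, underdispersion, is a property of the data and leads to a model whose error is on the safe side. The second, non-convergence, is a property of the fitting routine. It can occur with sparse cells or optimiser trouble while the counts are still over-dispersed. In that event the rule as written moves to a model that fixes the variance at the mean, which the same paragraph says such data usually violate. The standard error is then too small, the interval for the rate ratio too narrow, and a chance difference between the arms can be reported as significant.

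The SAP takes more care elsewhere. If multiple imputation fails (SAP 5.3), the number of iterations is raised first, and the model is changed only if that does not help. Section 5.7.5 has no such step.

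**Working it through.** SAP 5.7.5 gives no event rate, dispersion or power, so there is no figure of the plan's own to reproduce.

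**Inputs from the documents.** Two-sided 5% tests (Protocol 10.6.3); 84 and 42 subjects (SAP 5.1); 15 months, i.e. 1.25 years (SAP 2); age stratum as covariate and log time as offset (SAP 5.7.5).

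**Assumed.** Event rate 0.2 to 4 per subject-year and negative binomial dispersion k from 0 to 2, giving variance/mean = 1 + k × rate × 1.25.

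**Step 1: size of the error if Poisson is fitted to over-dispersed counts.** With variance/mean = phi, the Poisson SE is 1/sqrt(phi) of the true SE. The real level of a nominal 5% test is 2 × [1 − Φ(1.96/sqrt(phi))].

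| phi | SE too small by, 1 − 1/sqrt(phi) | 1.96/sqrt(phi) | Real level | Coverage of a 95% CI |
|---|---|---|---|---|
| 1.25 | 10.6% | 1.753 | 0.080 | 92.0% |
| 1.5 | 18.4% | 1.600 | 0.110 | 89.1% |
| 2 | 29.3% | 1.386 | 0.166 | 83.4% |

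**Step 2: simulation with no treatment effect.** There were 4,000 trials per scenario, with gamma-Poisson counts and Poisson regression on treatment and age stratum with log-time offset. The test used either the model SE or the SE multiplied by sqrt(Pearson chi-squared/df). A negative binomial dispersion estimate on its zero boundary served as a proxy for non-convergence.

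| Variance/mean | Unscaled Poisson error | Pearson-scaled error | Trials with a boundary fit |
|---|---|---|---|
| 1.00 | 0.045–0.053 | 0.046–0.056 | 58–63% |
| 1.625 | 0.113–0.124 | 0.046–0.051 | 0.1–0.4% |
| 2.25 | 0.175–0.187 | 0.045–0.052 | none |

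The unscaled column agrees with Step 1. Across all over-dispersed scenarios the scaled error was 0.041 to 0.057.

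**Step 3: error given a boundary fit.** In scenarios where boundary fits made up at least 3% of trials, the unscaled Poisson error given such a fit was 0.04 to 0.09. The mean Pearson ratio there was 0.91 to 0.98, so those samples look Poisson and the fallback does little harm.

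**Step 4: which correction.** Scaling without condition shrinks the SE when the Pearson ratio is below 1. In a separate simulation at 0.2 events per year and k = 1, the error given a boundary fit rose from about 0.06 unscaled to about 0.07 scaled. Scaling only when the ratio exceeds 1 uses the larger of the two SEs. It rejects only if both tests reject, so its overall error cannot exceed the smaller of the two columns in Step 2.

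**The case against.** The strongest reply is that the rule seldom does harm. The negative binomial model is fitted first. The usual benign cause of failure is a dispersion estimate near zero, and there Poisson is nearly right. At a variance/mean of 2.25 or more, no boundary fit was seen. That stands, and it sets the limits of the point. What remains is numerical failure despite real over-dispersion, and its frequency has not been estimated.

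Sparse hospitalisation counts may make failure likelier, but they also pull phi towards 1. At an assumed 0.2 per year the mean is 0.2 × 1.25 = 0.25, so phi = 2 would need k = (2 − 1)/0.25 = 4. This too stands.

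It can be said that the Pearson sentence hints at a scale correction. It does not exclude one, but no step says that the statistic enters the standard error.

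A reader might infer three stronger things that the documents do not support:

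- **That these comparisons will run at an inflated level, for instance 26% at phi = 3** (1.96/sqrt(3) = 1.132, level 0.258). That would hold only if Poisson were the planned model. It is a contingency.
- **That tested evidence on respiratory complications is at risk.** SAP 5.7.5 tests a pooled count of disease-related events and its hospitalised subset. Respiratory events are only presented as a category (SAP 6.1.8), and SAP 6.1.9 rules out testing of adverse events there.
- **That the underdispersion branch is equally faulty.** An unscaled Poisson SE is then too large, which is conservative.

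**Conclusion.** The point holds as a gap in a contingency rule. Section 5.7.5 lets non-convergence alone remove the allowance for over-dispersion that it otherwise considers necessary. Given a numerical failure with over-dispersion present, a nominal 5% test would run at about 11% (phi = 1.5) to 17% (phi = 2). Phi is assumed. The figures say nothing about how often the situation would arise, and they do not describe fits that fail because dispersion is near zero. With a tertiary, unadjusted endpoint outside the testing hierarchy, the trial's type I error control is untouched. This is a minor improvement worth making because it is cheap.

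**What to change.** Replace the non-convergence clause in SAP 5.7.5 with a short sequence:

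1. If the negative binomial model does not converge, refit with other starting values or another optimiser.
2. If it still fails, fit Poisson regression with the same covariate and offset.
3. Multiply the SE by sqrt(Pearson chi-squared/df) when that ratio exceeds 1, and keep the unscaled Poisson SE when it is 1 or below.

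The cost is a sentence or two in the SAP and one option in software already specified; the Pearson statistic is already to be computed. No data collection or sample size changes. The downside is slightly wider intervals whenever the ratio exceeds 1, including by chance, so the test is slightly conservative when the counts are truly Poisson. Settling this before unblinding avoids a later argument over which standard error to report.
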